**6-Oxycodone 5mg every 4 hours as needed for pain during the first 1-2 weeks postop**

After surgery, patients will be evaluated for the primary outcome of pain status at time points 2 hours and 24 hours using the numeric rating pain scale (0-10). Patient's nausea and vomiting will be evaluated by using a binary "yes" or "no" for nausea and recording the number of episodes of vomiting. The Apfel score will be used during statistical analysis to explore possible causes for differences in nausea and vomiting (0-4). Opioid consumption will also be recorded during the first 24 hours and converted to morphine milliequivalents using patient medical records. Patient data will then be compiled for statistical analysis.

Patients will be assessed routinely once every hour by the circulating nurse for the duration of their care in the hospital. Should a patient receive ambulatory care and depart from the hospital before 24 hours have elapsed, they will be contacted via telephone for assessment using the numeric rating pain scale (1-10) and post-op nausea and vomiting.

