## **6) Study Timelines\***

- *Participants will be active in the study for the 24 hours after the index knee replacement surgery.*
- *It will take about 6 months from the start of the study to recruit the total anticipated participants.*
- *We will allot 1 month after the final participant has completed the study for analysis and write up.*

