## 8) Study Endpoints\*

- *Primary endpoint – change in pain score at time points 2 hours and 24 hours after primary total knee arthroplasty for each group. The numeric pain rating scale will be used- a higher pain score would indicate higher pain levels. It is scaled from 0-10.*
- *Secondary endpoint - (1) Total opioid consumption in the immediate post-operative period (preoperative block versus postoperative block) (2) change in patient nausea scores and vomiting scores at time points 2 hours, and 24 hours (3) duration of hospital stay.*

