## **11) Adverse Events / Serious Adverse Events**

Any untoward or unfavorable medical occurrence in a human study participant, including any abnormal sign (e.g. abnormal physical exam or laboratory finding), symptom, or disease, temporally associated with the participants' involvement in the research, whether or not considered related to participation in the research will be recorded for the first 24 hours post-operatively.

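### Adverse events are promised for 24 hours, but the planned telephone contact after early discharge asks only about pain, nausea and vomiting, so the safety record would be incomplete for those patients

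*Combined protocol and SAP*

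**What the plan says.** Section 11 (Adverse Events / Serious Adverse Events) is broad. It covers untoward occurrences "including any abnormal sign (e.g. abnormal physical exam or laboratory finding), symptom, or disease", and these, "whether or not considered related to participation in the research will be recorded for the first 24 hours post-operatively". It does not say who asks, when, or with what question.

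Section 5 (Procedures Involved), after the list of standard medications, gives the means of observation. In hospital: "Patients will be assessed routinely once every hour by the circulating nurse for the duration of their care in the hospital". It then foresees early departure, "Should a patient receive ambulatory care and depart from the hospital before 24 hours have elapsed", and for that case says "they will be contacted via telephone for assessment using the numeric rating pain scale (1-10) and post-op nausea and vomiting". It sets no time for the call.

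Section 6 (Study Timelines) closes participation at the same point as the adverse-event window: "Participants will be active in the study for the 24 hours after the index knee replacement surgery". No later visit is described.

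Section 8 (Study Endpoints) lists "3) duration of hospital stay" as a secondary endpoint. Neither Section 8 nor Section 9 (Data Management) names an adverse-event endpoint or a comparison of adverse events between arms.

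**The concern.** The commitment in Section 11 is wider than the data collection in Section 5 that would have to deliver it. A patient still in hospital at hour 24 has been seen hourly throughout. A patient who went home earlier is asked about three things. A fall, leg weakness, bleeding, a drug reaction or an emergency visit between discharge and hour 24 would not be asked about, although each falls within Section 11. Those are also the hours without nursing supervision.

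Two things are at stake. First, the 24-hour record would be less complete for early leavers than the plan states. Secondly, any difference between arms in time to discharge would become a difference in how long adverse events are actively observed. The plan treats duration of stay as something that block timing might change, so this possibility cannot be set aside.

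**Working it through.** **Text check.** Setting the sections side by side:

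| Period | Planned observation | Adverse events covered |
|---|---|---|
| In hospital, up to hour 24 | Hourly nurse assessment (Section 5) | Content not specified; Section 11 requires all untoward events |
| After discharge, before hour 24 | One telephone contact, time not stated (Section 5) | Pain, nausea and vomiting; other events only if volunteered |
| After hour 24 | None (Section 6) | None |

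The gap is the second row, for events other than those three.

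**Size.** The plan states no figure to reproduce. It gives no share of patients discharged early, no discharge time and no adverse-event rate. What follows is illustration under assumptions.

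Inputs, all assumed: true 24-hour risk *p* of an event that the call does not ask about, 10% or 20%, equal in both arms; hour of early discharge *h*, 6, 12 or 18; share leaving early *f*; constant hazard; nothing volunteered after discharge.

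- Hazard: λ = −ln(1 − p)/24
- Recorded risk in an arm: (1 − f)·p + f·(1 − exp(−λh))

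Worked example, p = 0.10 and h = 12:

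- 1 − exp(−12λ) = 1 − 0.90^0.5 = 0.0513
- f = 0.30: 0.70 × 0.10 + 0.30 × 0.0513 = 0.0854
- f = 0.60: 0.40 × 0.10 + 0.60 × 0.0513 = 0.0708
- Recorded ratio: 0.0708/0.0854 = 0.83, against a true ratio of 1.00
- With the planned 42 per arm: 42 × 0.0854 = 3.6 and 42 × 0.0708 = 3.0 expected recorded events, against 4.2 true events in each arm

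Over the grid:

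| p | h | 50% early in both arms: share of events missed | 30% vs 60% early: recorded ratio | 20% vs 80% early: recorded ratio |
|---|---|---|---|---|
| 10% | 6 | 37% | 0.71 | 0.48 |
| 10% | 12 | 24% | 0.83 | 0.68 |
| 10% | 18 | 12% | 0.92 | 0.85 |
| 20% | 6 | 36% | 0.72 | 0.49 |
| 20% | 12 | 24% | 0.83 | 0.69 |
| 20% | 18 | 11% | 0.93 | 0.86 |

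A simpler check uses mean observed hours, f·h + (1 − f)·24. With 50% leaving at hour 6 this is 0.50 × 6 + 0.50 × 24 = 15.0 h, so 1 − 15/24 = 37.5% of observation time is lost, in line with the first row.

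The two consequences separate clearly. Loss of events needs only that some patients leave early. A ratio other than 1.00 needs, in addition, that the share or timing of early discharge differs by arm. With equal patterns the ratio is 1.00.

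**The case against.** The best defence is that silence is not exclusion. Section 11 is unconditional and not limited to inpatients. Section 5 describes how the study outcomes are collected and does not say that the call covers nothing else. On that reading the window is 24 hours for everyone, with only the method left open. This stands in part: the commitment does apply to all patients. But Section 5 is where staff will find what the call contains, and Section 11 gives them no other procedure, so a caller following the text would not ask about other events.

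A reader might infer that safety observation ends altogether at discharge, or that a later event has no way into the record. The documents do not support either. Nausea and vomiting are untoward symptoms and are collected on the call. An event that a patient mentions can be recorded under Section 11. Section 7 also refers to blinded data collectors, without stating their duties on adverse events. Consent and contact pages were not available for this review and may give patients a way to report. What is missing is planned, active questioning.

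A reader might also infer that a comparison of adverse events between arms would be biased. The plan contains no such comparison, and nothing in the documents shows that discharge times differ. Both arms receive the same block agent and volume and the same PACU orders (Section 5). Listing duration of stay as an endpoint shows that a difference is possible, no more. The absolute scale is also small: in the worked example the arms differ by about 0.6 of a recorded event.

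**Conclusion.** The concern holds as a gap in ascertainment. For patients discharged before 24 hours, planned collection of adverse events other than nausea and vomiting stops at discharge, apart from what they volunteer, and the 24-hour record stated in Section 11 would be incomplete for them. This rests on the text alone.

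Its size is unknown. Under the assumptions shown, with half of each arm leaving early, about 11% to 37% of such events would be missed; if nobody leaves early, none would be. These are upper figures for their scenarios, because they allow for no volunteered events.

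Inequality between arms is possible but not demonstrated. The recorded ratios of 0.71 to 0.93 (30% vs 60% early) and 0.48 to 0.86 (20% vs 80%) show what unequal discharge would do, not what is expected here.

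No planned endpoint, test or sample size is affected. The consequence is for safety reporting, and it is worth correcting because the remedy uses a call already in the plan.

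**What to change.** - **Section 5:** time the existing telephone contact at hour 24 and add one standard adverse-event question. An open question is enough; a few yes/no prompts are optional. Ask patients still in hospital the same question, in the same words, at hour 24.
- **Section 11:** state that this hour-24 question, in addition to in-hospital recording, is how events are ascertained for every patient regardless of discharge time.

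Every patient reached would then be asked about the same 24-hour window, and in the illustration the recorded ratio returns to 1.00 when true risks are equal.

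The cost is about two minutes per patient and a line on the data form. Slightly more events will be recorded. Treatment and sample size do not change.

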### **Simplified Apfel Score**

Risk Factors	Points
Female Gender	1
Non-Smoker	1
History of PONV	1
Postoperative Opioids	1
Sum =	0 ... 4

## **6) Study Timelines\***

- *Participants will be active in the study for the 24 hours after the index knee replacement surgery.*
- *It will take about 6 months from the start of the study to recruit the total anticipated participants.*
- *We will allot 1 month after the final participant has completed the study for analysis and write up.*

## **7) Study Design**

- The primary purpose of this project is in the treatment of pain around the immediate post-operative time after total knee replacement surgery. As a parallel experimental/interventional study design, patients will be randomized to either the control group (institution specific joint replacement pain protocol) or the intervention group (receiving the postoperative adductor canal block). Patients and those collecting the postoperative data will be blinded to eliminate bias in a 1:1 randomization process matching intervention group patients with control group patients. The surgeon will not be informed

ahead of time regarding which cohort a patient belongs to in an effort to reduce bias, though during the procedure may become privy to the group due to when the anesthesiologist places the block. The anesthesiologist will be informed the night before the respective procedure as to which group the patient was randomized into by one of the other non-primary surgeon members of the team. The randomization will be done using a random number generator. We aim to enroll 84 patients. If interested, the subject will be allowed to find out their group assignment when the study is over.

- Power Analysis:

Study Group Design: Two independent study groups

Primary Endpoint: Continuous

Data normally distributed

Alpha: 0.05

Power: 0.80

Total number of patients enrolled: 84

Based on similar study design [10], the standard deviation for pain scores was 3. Assuming a reasonable clinically significant difference of 2 on VAS score, this calculates to sample size of 35 in each group. Assuming attrition rate of 20%, 42 samples in each group will be obtained

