## 5) Procedures Involved\*

Study design: All patients who fulfill inclusion criteria, including undergoing a pregnancy test if a woman of childbearing age, undergoing total knee arthroplasty will be randomized to one of two groups to be given the standard orthopaedic joint replacement protocol including general anesthesia with the preoperative adductor canal block **or** the standard orthopaedic joint replacement protocol including general anesthesia except the adductor canal block will be given at the end of the procedure instead of the beginning. General anesthesia for the groups will be standardized, and no intraoperative analgesics given. Nerve blocks will be placed for both groups by anesthesiologists as is the standard protocol. All nerve blocks will be placed following the same procedural protocol with the same supplies under ultrasound guidance to ensure consistency and minimize variation. Nerve blocks in both groups will include the standard 20mL Ropivacaine 0.2% (local anesthetic) injected in the same manner. PACU orders will not differ between the groups and will be the standard procedure for total joint arthroplasty at the facility. Cases will be assigned randomly in a 1:1 fashion. A computer program such as Microsoft Excel will be employed for the randomization process.

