## 9) Data Management\*

We will perform a superiority test and examine the mean pain score differences at time points 2 hours and 24 hours after surgery as our primary outcome. A t test or Mann Whitney U will be performed to compare the means depending on the distribution of the data with confidence intervals. Secondary outcomes include postop nausea and vomiting scores and morphine equivalents received. We will compare these scores between groups similarly using t test or Mann Whitney U with confidence intervals.

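### Enrolment of 42 per group is 35 × 1.2 rather than 35 ÷ 0.8, so at the assumed 20% attrition the trial has about 77% power, not 80%

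*Combined protocol and SAP*

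**What the plan says.** The power analysis in section 7 (Study Design) lists two independent groups, a continuous and normally distributed primary endpoint, alpha 0.05 and power 0.80. The SD comes from an earlier trial of similar design, in which "the standard deviation for pain scores was 3". The effect size is set by "Assuming a reasonable clinically significant difference of 2 on VAS score". From these the plan concludes: "this calculates to sample size of 35 in each group. Assuming attrition rate of 20%, 42 samples in each group will be obtained". The overall figure is given as "Total number of patients enrolled: 84". Section 5 (Procedures Involved) fixes equal allocation: "Cases will be assigned randomly in a 1:1 fashion".

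Section 9 (Data Management) says "We will perform a superiority test", and names a t test or a Mann-Whitney U test, chosen according to the distribution of the data. The plan does not say whether alpha is one- or two-sided. It does not write out the inflation formula, and it gives no other attrition rate or further allowance.

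**The concern.** An attrition allowance has one job: to leave the required number of evaluable patients after the assumed fraction has been lost. That means dividing the required number by the fraction retained. Multiplying by one plus the attrition rate always falls short, because the losses come out of the larger, enrolled number. Here 42 equals 35 × 1.2 exactly, and it misses its target under the very attrition rate it was meant to cover.

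The base figure of 35 is also rounded down, so both departures lower power. What is at stake is the accuracy of the stated 0.80. That figure will be carried into the report and used to interpret a null result. There is no slack to absorb the shortfall either: the plan names two primary time points and an interim look, and the calculation shows no allowance for either.

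**Working it through.** **Inputs.** From section 7: difference δ = 2, SD σ = 3, alpha 0.05, power 0.80, attrition 20%, 42 per group, 84 in total. From section 5: 1:1 allocation. From section 9: t test or Mann-Whitney U. Sidedness is inferred in step 1.

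**1. Reproducing the base figure.** The normal formula for two means is n = 2(z₁₋α/₂ + z₁₋β)²(σ/δ)² per group.

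- Two-sided: 2 × (1.960 + 0.842)² × (3/2)² = 35.32, which rounds up to 36. The plan's 35 is this number rounded down.
- One-sided: 27.8, so 28 (28.5 by the t test). This does not reproduce 35, so a two-sided test is the reading that fits.
- Two-sided t test (noncentral t): 36.31, so 37.

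**2. Reproducing the inflation.**

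- 35 × 1.2 = 42.0, the plan's figure.
- 42 × 0.8 = 33.6 per group remaining (84 × 0.8 = 67.2 in total), below 35.
- 35/0.8 = 43.75, so 44 per group and 88 in total, if the plan's own 35 is kept.
- Attrition that takes 42 down to 35: 1 − 35/42 = 16.7%.
- Attrition that takes 42 down to 37: 1 − 37/42 = 11.9%.

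**3. Power at the relevant numbers** (two-sided alpha 0.05, δ/σ = 2/3, one comparison):

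| Evaluable per group | Normal approximation | t test |
|---|---|---|
| 33 | 0.773 | 0.760 |
| 33.6 (20% lost from 42) | 0.780 | 0.768 |
| 34 | 0.785 | 0.773 |
| 35 (plan's target) | 0.796 | 0.785 |
| 36 | 0.807 | 0.797 |
| 37 | 0.818 | 0.808 |
| 42 (no losses) | 0.863 | 0.855 |

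**4. Splitting the shortfall.** The inflation error alone takes t-test power from 0.785 (35) to 0.768 (33.6), a loss of 1.7 points; by the normal approximation the loss is 0.796 − 0.780 = 1.6 points. The rest of the gap to 0.80 comes from the low base.

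**5. Other expressions of the same result.** At 33.6 per group, the difference detectable with 80% power by the t test is 2.08 points instead of 2. If Mann-Whitney were applied to normal data (asymptotic efficiency 0.955), the effective size would be 33.6 × 0.955 = 32.1 per group and power about 0.748.

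**6. Size needed for 80% power at 20% attrition.** The answer depends on the base: 35/0.8 gives 44 (88 in total), 36/0.8 = 45 (90 in total), and 37/0.8 = 46.25 gives 47 (94 in total). Only the last reaches 80% by the t test. The 88 still leaves about 35 per group and t-test power of about 0.785.

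**The case against.** The best case for leaving the text alone is that the effect is small and conditional.

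- **Losses may be low.** Participation lasts 24 hours (section 6), and section 5 provides for hourly nursing assessment in hospital and a telephone call for patients discharged early. With no losses t-test power is 85.5%, and it stays above 80% until losses exceed about 13%. This stands, and the conclusion has to carry the condition. But 20% is the plan's own assumption, and the stated power should hold under it. If the sponsor expects less, the plan should say so.
- **The inputs are rougher than the error.** The SD of 3 is a round number from another trial. At 33.6 per group, an SD of 2.88 would restore 80% power and an SD of 3.2 would lower it to about 71%. This puts the size of the point in proportion, but uncertainty in an input does not excuse wrong arithmetic on it.
- **The base of 35 is a rounding and method matter.** This is largely right. Rounding 35.32 down costs 0.4 points by the normal approximation, and the rest of the gap to 37 is the difference between the normal and noncentral t calculations. On its own it would hardly be worth raising. The inflation error does not depend on it.
- **The Mann-Whitney figure assumes normality**, whereas the plan would choose that test when the data are not normal. So 0.748 is illustrative only, and the conclusion does not rest on it.
- **A restated 77% is not the whole story**, because it covers one test at full alpha. If alpha were split equally over the two time points (an assumption; the plan specifies no split), t-test power at 33.6 per group would be about 67%. This stands, and the restatement should therefore name its basis.

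**Conclusion.** The concern holds. The plan's 42 per group does not preserve its 35 at 20% attrition. Under that assumption power is about 77% by the t test (78% by the normal approximation), not 80%. The shortfall is 2 to 3 percentage points, of which about 1.7 come from the inflation error and the rest from the base figure.

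This rests on the plan's difference of 2 and SD of 3, a single comparison at two-sided alpha 0.05, and attrition of 20%. Sidedness is inferred from the plan's own 35. A one-sided test would have power of about 85.5% at 33.6 per group, but would leave the 35 unexplained. The two primary time points and the interim look are outside this calculation. The error is small but verifiable, and it should be corrected.

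**What to change.** Keep 84 patients and restate the power in section 7, for example: *For a single two-sided t test at alpha 0.05, with a difference of 2 and an SD of 3, 84 patients give about 77% power after 20% attrition (33 to 34 evaluable per group), and at least 80% power if attrition is no more than about 12% (37 or more evaluable per group).* This also puts the sidedness on record. It costs one sentence, a slightly less favourable stated power, and no extra patients or change in conduct. If the handling of the two time points or the interim look is later revised, the figure should be recalculated on that basis.

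If the sponsor prefers to hold 80% power at 20% attrition for the planned t test, enrolment becomes 47 per group, 94 in total, which is 10 more patients. Correcting the inflation alone on the existing 35 gives 88 in total, 4 more patients, but leaves t-test power at about 78.5%. The restatement is enough.

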## 8) Study Endpoints\*

- *Primary endpoint – change in pain score at time points 2 hours and 24 hours after primary total knee arthroplasty for each group. The numeric pain rating scale will be used- a higher pain score would indicate higher pain levels. It is scaled from 0-10.*
- *Secondary endpoint - (1) Total opioid consumption in the immediate post-operative period (preoperative block versus postoperative block) (2) change in patient nausea scores and vomiting scores at time points 2 hours, and 24 hours (3) duration of hospital stay.*

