## 2) **Objectives\***

The purpose of this project is to determine if a change in patient reported pain, nausea and vomiting after total knee arthroplasty can be observed with the substitution of post operative adductor canal block for a preoperative adductor canal block in the current established peri-operative pain protocol and if these changes lead to a decrease in opioid consumption (in morphine equivalents).

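### The primary endpoint is worded as a change in pain with no reference time, while the plan measures, sizes and tests pain scores; with no pre-operative score, a cheap gain in precision is missed

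*Combined protocol and SAP*

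**What the plan says.** All references are to the combined protocol and SAP.

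- **Section 8 (Study Endpoints)** gives the primary endpoint as "change in pain score at time points 2 hours and 24 hours" after surgery, stated for each group, on a 0–10 numeric scale. It does not say what the change is measured from.
- **Section 5 (Procedures Involved)** sets the measurement schedule: "After surgery, patients will be evaluated for the primary outcome of pain status at time points 2 hours and 24 hours". It adds that "Patients will be assessed routinely once every hour by the circulating nurse for the duration of their care in the hospital", without saying that these checks include a pain score or supply a baseline.
- **Section 6 (Study Timelines)** limits participation: "Participants will be active in the study for the 24 hours after the index knee replacement surgery".
- **Section 7 (Study Design)** bases the sample size on an SD of 3 for pain scores and a difference of 2 points. This gives 35 per group, raised to 42 per group for 20% attrition.
- **Section 9 (Data Management)** says the trial will "examine the mean pain score differences at time points 2 hours and 24 hours after surgery as our primary outcome". On the test it says: "A t test or Mann Whitney U will be performed to compare the means depending on the distribution of the data". No covariate is named.
- **Section 2 (Objectives)** also uses the word change, but for the effect of swapping one block timing for the other: the aim is to "determine if a change in patient reported pain, nausea and vomiting after total knee arthroplasty can be observed with the substitution".

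**The concern.** Section 8 and Section 9 do not describe the same quantity on a plain reading. A change attributed to each group sounds like a within-patient difference from some earlier score, whereas Section 9 compares the two groups' scores at each time point.

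The distinction can matter. Suppose one block timing lowered pain by 2 points at both 2 h and 24 h. The Section 9 comparison would show a 2-point difference at each time. A 24 h minus 2 h change would differ between groups by 2 − 2 = 0. The interim rule in Section 9 acts on a mean difference, so it too needs a clearly defined endpoint.

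The second issue is what the schedule leaves out. Without a pain score taken before the block, a change from baseline is unavailable, and so is a baseline-adjusted comparison of post-operative scores. That score cannot be collected once treatment has been given, so the choice has to be made prospectively.

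**Working it through.** **Step 1. What the data allow.** Section 5 schedules scores at 2 h and 24 h after surgery, and Section 6 begins participation after surgery. The hourly nurse checks are not described as a pain baseline. The candidate meanings of the Section 8 wording are:

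| Reading | Computable from scheduled data? | Fits Sections 7 and 9? |
|---|---|---|
| Change from a pre-operative score | No | No |
| Change from 2 h to 24 h within patient | Yes | No |
| Between-group difference in score at each time (the sense used in Section 2) | Yes | Yes |

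**Step 2. Reproduce the plan's sample size.** Inputs from Section 7: difference 2, SD 3, alpha 0.05, power 0.80. Sidedness is not stated; two-sided is assumed.

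n per group = 2 × (1.960 + 0.842)² × 3² / 2² = 2 × 7.85 × 2.25 = 35.3

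This is 36 after rounding up, against the stated 35 (noncentral t: 36.3). A one-sided test would need only 28. The stated figure is therefore reproduced, within rounding, as a two-sided comparison of pain scores. It was not derived from the SD of a change.

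**Step 3. Evaluable patients.** 35 × 1.2 = 42 enrolled per group. A 20% loss from 42 leaves 42 × 0.8 = 33.6 per group.

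**Step 4. What baseline adjustment would add.** With correlation r between the pre-operative and post-operative scores, the residual SD under ANCOVA is 3 × √(1 − r²). The documents give no r, so 0, 0.3 and 0.5 are assumptions. Power is from the noncentral t at 33.6 per group, two-sided 0.05, with noncentrality (2 / SD) × √(33.6 / 2). The one degree of freedom spent on the covariate is ignored.

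| Analysis | Residual SD | Noncentrality | Power |
|---|---|---|---|
| Unadjusted | 3.00 | 2.73 | 0.77 |
| ANCOVA, r = 0 | 3.00 | 2.73 | 0.77 |
| ANCOVA, r = 0.3 | 2.86 | 2.86 | 0.81 |
| ANCOVA, r = 0.5 | 2.60 | 3.15 | 0.87 |

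As a check that the pattern does not depend on the 33.6, the normal approximation at the plan's 35 per group gives 0.80 unadjusted, and 0.80, 0.83 and 0.90 adjusted at the same three values of r.

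**The case against.** The strongest reply is that this is one loose word and that the rest of the plan settles it. Section 5 calls the primary outcome pain status, Section 7 sizes on scores, Section 9 names the score comparison as primary, and Section 2 uses change for a between-group effect. An unadjusted two-sample comparison is valid in a 1:1 randomised trial, and not planning a baseline adjustment is not an error. Most of this stands, and it limits the point to a wording conflict and an optional improvement. It does not remove the conflict, because Section 8 is where the endpoint is defined and it speaks of change for each group.

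A reader might infer three stronger claims that the documents do not support:

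- **That the primary endpoint cannot be computed.** This is true only of change from baseline, and Section 8 never says from baseline. The Section 9 outcome can be computed as written.
- **That change must mean 24 h minus 2 h.** Section 2 offers another reading, and it is the one that Section 9 tests.
- **That the trial loses power because it analyses changes.** No change-score analysis is planned, and the 2-point effect in Section 7 is for scores, not for a difference in changes.

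It is also fair to object that ANCOVA should not displace the plan's provision for non-normal data. The fix keeps that provision.

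**Conclusion.** The point holds in limited form. Section 8 defines the primary endpoint in terms that do not match what Sections 5, 7 and 9 measure, size and test. The absence of a pre-operative score rules out both a change from baseline and a baseline-adjusted analysis. The trial remains analysable, and its stated sample size fits the Section 9 comparison.

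The gain forgone by not adjusting depends wholly on a correlation that the documents do not give. It is nil at r = 0, about 4 percentage points of power at r = 0.3 (0.77 to 0.81) and about 10 at r = 0.5 (0.77 to 0.87). These figures assume SD 3, a true difference of 2, a two-sided 0.05 test and 33.6 evaluable patients per arm. The change is worth making because it is cheap, not because the planned test is wrong.

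**What to change.** 1. **Section 8:** replace the change wording with pain score (NRS 0–10) at 2 h and 24 h. This aligns it with Sections 5, 7 and 9. The secondary nausea and vomiting endpoint uses the same undefined term and should be reworded in the same way.
2. **Section 5:** add one NRS pain score before randomisation, or at least on the day of surgery before any block. A score taken after the pre-operative block would be affected by treatment in one arm and could not serve as a baseline. Amend Section 6 so that the participation window covers this assessment.
3. **Section 9:** make the primary comparison at each time point an ANCOVA with treatment and pre-operative NRS as terms, reporting the adjusted mean difference and its 95% CI. Keep a rank-based analysis as the fallback or sensitivity analysis for non-normal data. State that the mean difference in the interim rule refers to the same endpoint.

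The first step costs only wording and stands even if the sponsor declines the other two. Steps 2 and 3 cost one pre-operative question and one extra data item per patient, with no additional patients.
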